6.0 Study Intervention

All study participants will continue to receive standard-of-care cancer screening over the course of this study, as they have prior to study enrollment. Study participants randomized into the experimental arm will provide blood samples 3 times a year for 4 years. cfDNA sequencing will be performed on blood samples collected from participants in the experimental group. Results of the cfDNA sequencing (either “cancer signal detected” or “cancer signal not detected”) will be communicated to the participant by a designated member of the study team. We expect up to approximately 5-10% of participants per year in the experimental arm will receive a “cancer signal detected” result, which will trigger follow-up diagnostic investigations to confirm if cancer is present or not (outlined in Appendix A: “Cohort Specific Diagnostic Workflows”). The type of follow-up diagnostic investigations will be consistent with standard-of-care recommendations.

7.0 Assessment of Efficacy and Safety

There is a possibility that the sequencing tests (sWGS, targeted panel, cfMeDIP) are less sensitive than standard-of-care screening. We will continuously monitor the concordance between cfDNA assay results and standard-of-care surveillance results. Confirmation of a cancer diagnosis will be supported by imaging confirmation, pathologic confirmation, or another form of clinical confirmation deemed appropriate by the study investigator. Yearly, we will evaluate:

- the percentage of cancers found by standard-of-care screening missed by the cfDNA assay.
- the percentage of positive cfDNA results where no cancer is detected on any follow-up diagnostic investigations.

If we determine that one of the tests are consistently underperforming (e.g. if 50% of cancers found by standard of care screening are missed by cfDNA assay), we will consider discontinuing the underperforming assay, and replacing it with an alternative validated test (e.g. plasma WGS). If we change one or more of the assays over the course of the study, participants will be notified of this change verbally by a study team member. If no alternative test is available, we may decide to end the study early.

The Study Doctor will perform the following tasks to ensure the safety of subjects and the good conduct of the study, on a monthly basis:

- Review the study binder to ensure all documents and communications are up to date
- Review the Inclusion/Exclusion forms for completeness and compliance to study protocol
- Monitor the accrual rate and recruiting efforts
- Monitor the number of ‘false positive’ results, and the number of subsequent diagnostic investigations undergone by the participant
- Monitor participant compliance to routine cancer screening protocols

Study related adverse events will be documented and reported to the UHN REB, as per the standard institutional procedure.

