2.0 Background Information

2.1 Background and Rationale

Early cancer detection is the surest path to survival, even cure. As cancer progresses, genetic changes continue to amass, thereby making late-stage cancers more aggressive, harder to eradicate, and more lethal. People who are affected by a hereditary cancer syndrome (HCS) have this lived experience, as they are born with a genetic change that puts them at high risk for developing multiple cancers throughout their lifetime. Over 200,000 Canadians harbor mutations in one of the >100 genes that cause an HCS, some facing a 100% lifetime risk of developing cancer^{1,2}. To find these cancers in time for effective treatment, all of these carriers undergo highly specific medical imaging and physical exams on a biannual or annual basis, often travelling 100s of kilometers at significant personal stress, expense, and time investment. Sadly, many of these patients receive late-stage cancer diagnoses, necessitating immediate and often radical surgeries, radiation treatments, or enrollment in experimental clinical trials.

People who carry an HCS genetic variant describe themselves as “ticking cancer time bombs” as they await the accumulation of mutations during their lifetime that trigger cancer development³. Depending on cancer type, individuals may be able to enroll in publicly-funded annual surveillance programs that are cancer-type specific and entail an array of comprehensive clinical exams and imaging modalities, such as full-body MRI, colonoscopies and mammograms. In HCS that predispose cancers for which early detection has not yet been possible, prophylactic surgeries are recommended, such as removal of breasts, ovaries, and fallopian tubes for carriers of Hereditary Breast and Ovarian Cancer (HBOC), removal of uterus and ovaries in Lynch Syndrome (LS), and gastrectomy for carriers of Hereditary Diffuse Gastric Cancer (HDGC)^{4,5,6}. These life-altering surgeries place a heavy psychological and physical burden on patients, particularly those of childbearing age who face uncertain timing of growing a family versus potential development of a cancer.

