cfDNA sequencing assay, and results will be communicated to participants by the study team. Participants who receive a “positive” cfDNA assay result will be offered follow-up diagnostic procedures to confirm or rule out the presence of a malignancy. The diagnostic investigations are outlined in “Cohort Specific Diagnostic Workflows”, appended to this protocol. If an abnormality is identified by a diagnostic investigation done in follow-up to a “positive” cfDNA assay result, additional investigations (e.g., imaging or biopsy) will be performed as part of the participants clinical care, and will be guided by the participant’s clinical team, or study investigator. All participants will be followed by the study team for a minimum of 5 years, from their first blood collection. To assess the efficacy of the cfDNA assay, we will compare cfDNA assay results to the results of the participants standard of care cancer surveillance results.

Lastly, we will use questionnaires and semi-structured interviews to explore participants’ experiences with cfDNA testing, to understand perceptions of the clinical utility of cfDNA tests for HCS management and identify factors facilitating or impeding the uptake of this test in HCS management and patient decision making.

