4.11 Endpoints

The endpoints of this study are:

1. To assess the performance of the cfDNA assay for cancer detection in patients with HCS, including assay sensitivity, specificity, PPV, and NPV. The test performance endpoint is a diagnosis of cancer and will be assessed at multiple points during the study (at a minimum yearly). Cancer diagnosis will be confirmed by imaging, pathology, or other confirmation deemed appropriate by the treating physician.
2. To assess the time to cancer diagnosis using cfDNA sequencing compared to controls.
3. To assess the detection rate of cancer with no standard-of-care screening available (e.g., pancreatic cancer, endometrial cancer) using cfDNA sequencing.
4. To assess patient reported outcomes (including anxiety, empowerment, distress, risk perception) using validated scales administered before, during, and after the study.

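### The one example of assay underperformance counts only cancers found by standard-of-care screening, so it overstates the miss rate when cfDNA finds cancers first

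*Protocol*

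**What the plan says.** Protocol section 7.0 raises the possibility that the sequencing tests are less sensitive than standard-of-care (SOC) screening. It promises that "We will continuously monitor the concordance between cfDNA assay results and standard-of-care surveillance results" and names two yearly measures. One is "the percentage of cancers found by standard-of-care screening missed by the cfDNA assay". The other is the share of positive cfDNA results for which the work-up finds no cancer. Only the first has a number attached, as an example of consistent underperformance: "if 50% of cancers found by standard of care screening are missed by cfDNA assay". The team would then consider dropping that assay for another validated one, and "If no alternative test is available, we may decide to end the study early".

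Two other places bear on this. Under section 4.1, experimental-arm participants with a positive result "will be offered follow-up diagnostic procedures to confirm or rule out the presence of a malignancy", so cfDNA can lead to a diagnosis between screening visits. Section 4.11 plans sensitivity, specificity and predictive values against any confirmed cancer: "The test performance endpoint is a diagnosis of cancer and will be assessed at multiple points during the study (at a minimum yearly"). Nothing in section 7.0 links that measure to the decision to replace the assay or stop.

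**The concern.** A miss rate among screening-found cancers would be a fair measure if cfDNA results were withheld until screening had taken place. Here they are returned and acted on. A cancer that cfDNA flags, and that is diagnosed before the next screening visit, is never found by screening and so is not in the denominator. A cancer that cfDNA misses waits for the visit and is counted. The denominator loses cfDNA's successes and keeps its failures.

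Earlier detection is the primary objective, so the more often the assay achieves it, the worse this percentage looks. At stake is the quality of one input to a decision that could change the assay mid-trial or end the study.

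**Working it through.** The 50% is a chosen example with no derivation, so there is no figure of the plan to reproduce. The check is how far the percentage can sit from the true miss rate.

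**Formula.** Let s be cfDNA's true sensitivity among screened cancers, and p the share of cfDNA-positive cancers diagnosed before the next SOC visit. Per screened cancer, s·p leave the denominator and 1 − s are missed, so

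reading = (1 − s) / (1 − s·p).

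It reaches 50% when p = (2s − 1)/s: 0.33 at s = 0.60, 0.57 at s = 0.70 and 0.75 at s = 0.80.

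**Inputs from the Protocol.**
- Draws every four months (section 4.1): 365.25/3 = 121.75 days.
- Report within 45 days of sample receipt (section 4.5), disclosure within 2 weeks (section 4.6): 45 + 14 = 59 days, ignoring transit.
- SOC visits: "all of these carriers undergo highly specific medical imaging and physical exams on a biannual or annual basis" (section 2.1), taken as every 6 or 12 months.

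**Assumptions.** Cancers become detectable uniformly over time. SOC finds every screened cancer present at a visit. Work-up takes W days. At first, cfDNA turns positive as soon as the cancer is SOC-detectable, and one draw coincides with the visit.

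**Annual visits.** Draws fall at days 121.75, 243.5 and 365.25 (the visit).
- Cancers arising in the first third are diagnosed before the visit if 121.75 + 59 + W < 365.25, so W < 184.5.
- Those in the second third need 243.5 + 59 + W < 365.25, so W < 62.75.
- Those in the last third are first drawn at the visit.

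Hence p = 2/3 for W up to 62, 1/3 for 63 to 184, and 0 beyond.

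**Six-monthly visits.** The same steps give p = 1/2 for W < 1.875 days, 1/6 for 2 to 62, and 0 beyond.

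| p | true miss 20% | true miss 30% | true miss 40% |
|---|---|---|---|
| 2/3 | 42.9% | 56.3% | 66.7% |
| 1/2 | 33.3% | 46.2% | 57.1% |
| 1/3 | 27.3% | 39.1% | 50.0% |
| 1/6 | 23.1% | 34.0% | 44.4% |
| 0 | 20% | 30% | 40% |

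In counts, for 100 screened cancers with s = 0.70 and p = 2/3: 46.7 are found cfDNA-first, 23.3 are found at the visit with a positive cfDNA result, and 30 are found at the visit and missed by cfDNA. The section 7.0 percentage is 30/53.3 = 56%; the true miss rate is 30/100.

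**Draws at random times relative to visits** (simulation of 2,000,000 onsets, s = 0.70, W = 0, 30, 60): annual 56.6%, 51.1%, 46.5%; six-monthly 39.5%, 34.8%, 32.0%.

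**If cfDNA turns positive later than SOC detectability** (annual, aligned draw, W = 30, s = 0.70): a 60-day lag gives p = (243.5 − 60)/365.25 = 0.502 and a reading of 46%. A 120-day lag gives p = 123.5/365.25 = 0.338 and 39%. With six-monthly visits and a 60-day lag the reading is 30%.

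**If diagnosis comes only by the PET-CT step in section 4.6**, which waits for the next scheduled draw (W about 122 days), the reading is 39% with annual and 30% with six-monthly visits.

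**The case against.** The strongest reply is that little is fixed here. The 50% is an example, the required pattern is consistent underperformance, and both actions are discretionary. Concordance is monitored continuously, false positives monthly, and section 4.11 gives all-diagnosis sensitivity at least yearly. The team would hold the figures that correct the percentage. This stands, and it limits the weight. A reader might infer that the rule would stop a good trial; the text does not support that, because nothing in it is automatic.

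The size is also open to challenge. With six-monthly visits, slow work-up or a lag in cfDNA positivity the bias shrinks, in some cases to nothing, and a true 20% never reads above 43% in the aligned-draw table. This stands too.

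A reader might infer an equal bias in the other direction, because cancers without SOC screening and those presenting with symptoms are not counted either. If 10% to 30% of cancers were of this kind (assumed) and 70% were missed (assumed), an overall miss rate of 34% to 42% would sit behind a reading of 30%; if all were missed, 37% to 51%. But section 7.0 asks how cfDNA compares with SOC screening, and unscreened cancers cannot inform that. They have their own endpoint: "To assess the detection rate of cancer with no standard-of-care screening available (e.g., pancreatic cancer, endometrial cancer) using cfDNA sequencing". This is a limit on scope, not a bias in that comparison.

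Nor is every cancer found in a cfDNA work-up certain to be the source of the signal; some may be coincidental.

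The objection fails on one point. The percentage is the only measure in section 7.0 with a number and a consequence attached, and it moves the wrong way when the assay succeeds. Later detail on timing or counts would not cure that.

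**Conclusion.** The point holds as a biased decision input of minor to moderate weight. Section 7.0's example overstates the miss rate when cfDNA brings diagnoses forward. At an assumed true miss rate of 30% it reads from 30% to about 57%. It passes 50% only with annual SOC visits, quick work-up and cfDNA positivity close to the time of SOC detectability. At a true 40% less is needed: p = 1/3 already brings it to 50%. The Protocol gives neither the assay's sensitivity nor the split of detection routes, so these figures illustrate the mechanism and do not forecast the trial.

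**What to change.** Change section 7.0 only.

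- Base the underperformance judgement on the section 4.11 yardstick: the cfDNA miss rate with all confirmed experimental-arm cancers, by any route, as denominator. Report it cumulatively each year. At 5% to 10% of 500 participants (section 8.0) there would be 25 to 50 cancers over the study, too few to judge year by year.
- Count a cancer as missed if no draw in a fixed period before diagnosis, for example 12 months, was positive.
- Report the rate for each first-line test (sWGS and the panel) and for the combined result, since the decision concerns individual tests. Give it separately for cancers with no SOC screening.
- Show the present SOC-found miss percentage and the number of cfDNA-first cancers beside it, and keep the work-up-negative percentage.
- Do not compare cfDNA-only with SOC-only cancers as a test of sensitivity. SOC has no chance to find a cancer already diagnosed through cfDNA. In the 100-cancer example that comparison shows 46.7 against 30 in favour of cfDNA, although SOC would have found every one.

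The cost is one extra yearly tabulation from results and dates already collected under section 4.8 (Collection of Clinical Data). The all-cancer rate somewhat favours cfDNA, because a positive result triggers verification; this is why the SOC-found percentage stays beside it.

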8.0 Statistics

We will compare the cancer detection rate between control and experimental cohorts. Analysis will be stratified by the type of the tumours detected within each HCS, as well as across the entire cohort. Between the cohorts, we will first compare the cancers detected to ascertain whether cfDNA testing results in a more sensitive detection of clinically confirmed cancers, as well as calculate negative and positive predictive values of cfDNA findings as confirmed by clinical testing (MRI, ultrasound, biopsy, protein biomarkers, etc.). This analysis will also ascertain whether cfDNA is more or less effective at detecting specific cancer types compared to standard-of-care screening alone.

We will also conduct comparisons that compare categorical (e.g. cancer stage) and continuous time course data (e.g. time to symptom development, time to treatment, and time on treatment). The first comparison is a stage shift analysis, whereby we will assess whether cancers are being detected at earlier stages using cfDNA versus screening results from the same programs. Categorical variables of stages I-IV within each cancer type as defined by NCCN criteria will be compared using Pearson's χ^2 test. Binary comparison of “early” and “late” stage across all cancer types will be performed using Fisher Exact test. The second comparison will be calculation of the time to first treatment relative to the date of the last annual clinical screening visit. This comparison of continuous variables using the t-test will establish whether triannual cfDNA testing accelerates off-cycle clinical follow-up and medical treatment compared to waiting for annual clinic visits. The third comparison will compare mortality and morbidity specifically for pancreas, esophagus, brain, lung, and stomach cancers. We will calculate the time between detection of a cancer and when patient manifest symptoms of cancer (morbidity 1), how long patients are afflicted with cancer symptoms after detection and during treatment (morbidity 2), and how long a patient undergoes treatment before succumbing to disease (mortality) or, in the case of effective treatments, the time until treatment is discontinued, or patients transition to the outpatient setting. Continuous variables will be compared by t-test.

Power analysis is based on the primary outcome of improved cancer detection at various diagnosis rate scenarios of the study cohort at the end of the study, range with current 5% detection rate for all HCS without cfDNA modeling, up to 10% should cfDNA improve

detection. Based on the power analysis, our study with 1,000 patients will achieve >97% statistical power to detect at least 2% increased diagnosis rate attributable to cfDNA testing with 2-sided significance level at 0.05.

Lastly, analysis of the survey data will be led by [name] at Unity Health and [name] at Memorial University. DTAs will be established and signed by all institutions, prior to sharing of any data. Baseline adjusted mean differences between groups with 95% confidence intervals will be calculated for test-specific distress and uncertainty, generalized distress, anxiety, empowerment and quality of life; a regression framework for hypothesis-generating purposes will be used. Estimates of variance and correlation among emotional outcomes and empowerment, and quality of life and between groups will be determined. Proportion of cases and drop outs from rural/remote geographic regions across arms will be compared using a chi square test. P-values are set at 0.05 (two-tailed).

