4.1 Overall Study Design

We are conducting a randomized control trial to assess the use of cfDNA analysis in cancer surveillance protocols for patients with HCS. We will recruit 1,000 patients across Canada with a known/suspected genetic diagnosis of one of the following HCS: HBOC, LS, NF1, LFS, PALB2, or HDGC that are receiving standard-of-care clinical assessment for cancer by a managing physician under a provincial screening program or cancer surveillance protocol.

The study design is illustrated in Figure 1. At study enrollment, participants will be randomized to a control cohort (n=500) or an experimental cohort (n=500), stratifying for genetic HCS background. All participants in the experimental cohort will provide blood samples tri-annually (every four months) for four years, either at the study hospital, or at a local blood laboratory (e.g., LifeLabs or Dynacare). Whenever possible, patients will have research blood collected at the same time as routine blood collections for clinical purposes, to avoid additional venipunctures. Participants randomized to the control cohort will have the option to donate samples to the CHARM Consortium Biobank, for use in future research. Participants in the control cohort can donate between 1-3 blood samples a year, for the duration of the study.

Participants in both the control and experimental cohorts will continue to receive standard-of-care cancer surveillance according to current guidelines, as they were prior to study enrollment. Blood samples from the experimental cohort will be subject to a

Figure 1. Study Design.

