4.9 Randomization and Measures to Minimize Bias

Cancer risks are different for the 5 HCS cohorts we will enroll in this study. Participants will be randomized into the control and experimental arms based on their HCS diagnosis, to achieve roughly the same number of participants from each HCS cohort in each arm of the study. To avoid over-stratification, we will not randomize participants based on other factors (such as age, prophylactic surgery, cancer history etc.). However, these other factors also influence cancer risks, and we will collect this information, to minimize bias in our subsequent analysis.

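### The between-arm cancer detection comparison is to be stratified by tumour type, an outcome, and no overall comparison stratified by the randomisation factor (HCS) is stated

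*Protocol*

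**What the plan says.** Section 4.1 has 1,000 participants "randomized to a control cohort (n=500) or an experimental cohort (n=500), stratifying for genetic HCS background". Section 4.9 gives the reason: "Cancer risks are different for the 5 HCS cohorts we will enroll in this study". It declines to stratify on age, prophylactic surgery or cancer history, but adds that "these other factors also influence cancer risks, and we will collect this information, to minimize bias in our subsequent analysis".

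Section 8.0 opens with a comparison of the cancer detection rate between the two arms and then states: "Analysis will be stratified by the type of the tumours detected within each HCS, as well as across the entire cohort". It names no test for that comparison. The tests it does name belong to other outcomes: stage I-IV "within each cancer type as defined by NCCN criteria will be compared using Pearson's" chi-square test, early versus late "stage across all cancer types will be performed using Fisher Exact test", and, for treatment timing and morbidity durations, "Continuous variables will be compared by t-test". Survey outcomes are to be baseline-adjusted in a regression framework.

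Sections 2.4, 4.1 and 5.1 each list six conditions: HBOC, LS, NF1, LFS, PALB2 and HDGC.

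**The concern.** A stratum for comparing randomised arms must be fixed at randomisation, so that everyone belongs to one and treatment cannot move anyone between them. Tumour type fails on both counts. Undiagnosed participants have none, and the trial expects the blood test to change which tumours are found: section 3.1.2 hopes for more cancers of types that current screening detects poorly. Groups formed by detected tumour type are therefore selected after randomisation, partly by the intervention.

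The baseline factor that the design does treat as prognostic is not stated as a stratifier of the overall comparison. At stake are a clear definition of the main between-arm contrast and a little efficiency. The count of five against six leaves open which strata are used to randomise, and hence which to use in the analysis.

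**Working it through.** **1. Can tumour type be a stratum?** Section 8.0 takes 5% detection without cfDNA, up to 10% with it, and an increase of at least 2% as the target (read here as 5% v 7%). With 500 per arm:

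- 5% v 7%: 25 + 35 = 60 cancers, so 940 of 1,000 participants have no tumour type.
- 5% v 10%: 25 + 50 = 75 cancers, so 925 of 1,000 have none.

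Among people defined by having a detected tumour of a given type, the detection proportion is 100% in both arms by construction, so there is nothing to compare. To obtain a rate, the denominator must be all randomised participants. That is a type-specific incidence, not a stratified analysis.

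The cells are also small. Spread evenly over six syndromes, there are 60/6 = 10 to 75/6 = 12.5 cancers per syndrome, both arms together. With an assumed four tumour types per syndrome, there are 60/24 = 2.5 to 75/24 = 3.1 per cell.

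**2. What does leaving out HCS cost?** The protocol gives no risk by syndrome, so every syndrome-level figure below is an assumption.

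*Variance explained.* Take risks of 2, 5, 8 and 12% in 40, 30, 20 and 10% of participants. The mean is 0.008 + 0.015 + 0.016 + 0.012 = 0.051. The between-stratum variance is 0.4(0.031)² + 0.3(0.001)² + 0.2(0.029)² + 0.1(0.069)² = 0.00103. Divided by 0.051 × 0.949 = 0.0484, this is about 2% of the outcome variance.

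*Reference power.* The pooled two-proportion formula is Φ{[|p2 − p1| − 1.96√(2p̄q̄/n)] / √[(p1q1 + p2q2)/n]}. For 5% v 7% and n = 500 it gives (0.02 − 0.0294)/0.0150 = −0.629, or 26.5%. For 5% v 10% it gives 85.2%. The protocol's figure of more than 97% for a 2% increase is not reproduced. That is a separate matter, and this point does not rest on it.

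*Simulation.* 40,000 trials per scenario; 500 per arm; six strata balanced between arms with shares 40/30/10/10/5/5%; a common odds ratio of 1, 1.43 or 2.11. The unadjusted two-proportion z-test is set against Cochran-Mantel-Haenszel (CMH), z = Σ(x1 − m/2) / √Σ[m(2n − m)n² / ((2n)²(2n − 1))], where, in each stratum, n is the number per arm, m the cancers in both arms and x1 those in the experimental arm.

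| Assumed control risks by stratum (%) | Overall rates | Unadjusted | CMH |
|---|---|---|---|
| 4, 4, 4, 15, 4, 4 | 5.1 v 5.1 | 4.7% | 5.1% |
| | 5.1 v 7.1 | 24.7% | 25.8% |
| | 5.1 v 10.0 | 84.2% | 85.0% |
| 3, 4, 5, 16, 4, 5 | 5.0 v 5.0 | 4.5% | 4.9% |
| | 5.0 v 6.9 | 24.1% | 25.5% |
| | 5.0 v 9.6 | 82.7% | 83.8% |
| 1, 2, 5, 30, 4, 5 | 5.0 v 5.0 | 3.2% | 5.0% |
| | 5.0 v 6.6 | 16.6% | 22.2% |
| | 5.0 v 8.7 | 67.6% | 75.1% |

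Rows with equal rates show type I error; the others show power. The gain is 0.8 to 1.4 points under moderate spread, and 5.6 and 7.5 points under extreme spread. The unadjusted test errs on the conservative side.

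**3. Five or six strata?** Section 4.9 says five; counting the list in sections 2.4, 4.1 and 5.1 gives six. The protocol does not say whether two of the six are merged.

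**The case against.** The strongest reply is that the sentence is loosely worded rather than wrong. It can be read as the detection rate of each tumour type, by arm, within each syndrome and overall. That reading fits the secondary objective in 3.1.2 and the third endpoint in 4.11, and with all randomised participants as the denominator it is a valid contrast. This stands as a charitable reading, but the text does not state that denominator, and it calls tumour type a stratifier.

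A reader might infer that HCS is ignored. It is not: the same sentence carries the analysis out within each HCS. What is absent is an HCS-stratified overall estimate.

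A reader might also infer that the arms as a whole will be compared by plain chi-square, Fisher and t-tests. The protocol does not say so. Those tests are assigned to stage, time to treatment and morbidity or mortality durations, all among diagnosed cases. For the detection rate no test is named, and the test and covariate list may properly sit in a statistical analysis plan that is not shown. Nor are all analyses unadjusted, since the survey outcomes are baseline-adjusted.

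Finally, stratifying every comparison by HCS and adding three covariates would have a cost: with 60 to 75 expected cancers, models among cases would be sparse and unstable. This stands, and it limits the fix.

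**Conclusion.** The point holds in limited form. The only stratifier that section 8.0 states for the between-arm detection comparison is an outcome, and it does not correspond to the factor used to randomise. The conflict between five and six cohorts is also real.

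The numerical consequence is modest: about 1 point of power under moderate spread of risk, and about 6 to 7.5 points only if one syndrome carries a risk near 30% and the largest ones 1 to 2%. All of this rests on assumed syndrome shares and risks and a common odds ratio. The stronger inference, that leaving HCS out biases the overall comparison or inflates type I error, is not supported. HCS is balanced by design, and the unadjusted test is, if anything, slightly conservative. This presumes that all randomised participants are analysed as randomised.

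HCS stratification would not turn the stage, time-to-treatment and morbidity comparisons into randomised contrasts, because they are made among people selected by diagnosis.

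**What to change.** - In section 8.0, state that the overall comparison of detection rate or time to diagnosis includes all randomised participants and is stratified by the HCS randomisation strata, for example by Mantel-Haenszel or a stratified log-rank test or Cox model.
- Optionally add a sensitivity analysis of that same comparison adjusted for age, prior cancer and prophylactic surgery at baseline. This would give section 4.9's commitment a counterpart in the analysis.
- Replace stratification by tumour type with the incidence of each type per randomised participant, by arm, as a descriptive secondary analysis.
- Reconcile the five cohorts of section 4.9 with the six in 2.4, 4.1 and 5.1, and use one list for randomisation and analysis.

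The cost is a change of wording. The baseline variables are already to be collected under section 4.8, and no extra participants or visits are needed. If the randomisation system already uses a particular list, the text should be brought into line with it.

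### The stage-shift tests count only diagnosed cancers, so extra early diagnoses can produce a significant shift with no fall in late-stage disease; the per-type chi-square is also too sparse to rely on

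*Protocol*

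**What the plan says.** Protocol section 8.0 (Statistics) describes a stage-shift analysis in which "we will assess whether cancers are being detected at earlier stages using cfDNA versus screening results from the same programs". Two tests are fixed:

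- Per type: "Categorical variables of stages I-IV within each cancer type as defined by NCCN criteria will be compared using Pearson's" chi-square test.
- Pooled: a two-category comparison of early and late "stage across all cancer types will be performed using Fisher Exact test".

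The section does not say which stages count as early or late. It gives no category for participants without a diagnosis and no comparison of late-stage cancers per randomised participant. Its opening comparison, the detection rate by arm, counts all cancers without separating stage.

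The design facts that matter are:

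- Section 4.1: "participants will be randomized to a control cohort (n=500) or an experimental cohort (n=500), stratifying for genetic HCS background".
- Section 8.0 on expected diagnoses: "range with current 5% detection rate for all HCS without cfDNA modeling, up to 10% should cfDNA improve" detection. The same paragraph ties these rates to the end of the study, in a sentence that begins "Power analysis is based on the primary outcome of improved cancer detection at various diagnosis rate scenarios of the study cohort at the end of".
- Section 3.2 hypothesises that more cancers will be found, and at earlier stages.
- The Protocol Summary (Study Design) lists stage shift, together with clinical impact on mortality and morbidity, as the second of three aims.

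**The concern.** Stage exists only for people who have been diagnosed, so both tests condition on an event that happens after randomisation and that the intervention is meant to change. If cfDNA testing adds early or indolent cancers to one arm, the late-stage share in that arm falls because its denominator grows. The number of late-stage cancers per 500 randomised need not change at all.

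A significant result would then describe a different mix of detected cancers. It would not show that late-stage disease was reduced, which is what the clinical-impact aim in the Protocol Summary needs. No other analysis in section 8.0 compares late-stage incidence between the arms as randomised.

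A second, separate weakness is that the per-type Pearson test spreads a small number of cancers over many cells, where its large-sample approximation is unreliable.

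**Working it through.** **Inputs from the Protocol.** 500 per arm (section 4.1); 5% diagnosed without cfDNA and up to 10% with it by the end of the study; a planned 2-point gain, two-sided 0.05 (section 8.0).

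**Assumptions.** The Protocol gives neither the late-stage share nor the number of cancer types. I take 30-60% of control cancers as late stage and 5-10 types.

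**The plan's own figure.** Nothing is stated for the stage tests. The only power figure is more than 97% for a 2-point gain. The usual two-proportion formula with 500 per arm gives 26.5% for 5% versus 7% and 85.2% for 5% versus 10%, so it is not reproduced. That is a separate matter; only the case counts are used here.

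**Case counts.** 500 × 0.05 = 25 control. Experimental: 500 × 0.07 = 35, or 500 × 0.10 = 50. Total 60 or 75, or 50 if there is no gain.

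**Single tables: 25 versus 50 cases, same number of late cancers in each arm**

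| Late per arm | Late share, control v cfDNA | Fisher p |
|---|---|---|
| 10 | 40% v 20% | 0.096 |
| 12 | 48% v 24% | 0.064 |
| 13 | 52% v 26% | 0.039 |
| 15 | 60% v 30% | 0.023 |

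With 25 versus 35 cases, late counts of 8, 10, 12 and 15 give p from 0.29 to 0.56. One table is too sensitive to a single count, so repeated trials are more informative.

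**Repeated trials.** For late share s and experimental rate r, late cancers are Binomial(500, 0.05s) in both arms. Early cancers are Binomial(500, 0.05(1 − s)) in control and Binomial(500, r − 0.05s) in the cfDNA arm. Late-stage incidence is thus equal and all extra cancers are early. Percentage with Fisher p < 0.05 (4,000 runs):

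| s | Case-only, 5% v 7% | Case-only, 5% v 10% | Late stage per 500 randomised |
|---|---|---|---|
| 30% | 9.0 | 27.9 | 2.7-2.8 |
| 40% | 11.2 | 39.6 | 3.2-3.4 |
| 50% | 16.4 | 51.0 | 3.0-3.3 |
| 60% | 21.6 | 66.4 | 3.5-3.6 |

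A repeat with 20,000 runs, counting only case-only results that favour cfDNA, gave 8.5-21.2% and 28.0-65.3%. With 5% in both arms the case-only test rejects in about 3-4%, so the excess comes from the unequal denominators.

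**Sparse cells.** The per-type table has 4 stages × 2 arms = 8 cells. Expected counts of 5 throughout, the usual rule, need 8 × 5 = 40 cases of one type even with perfectly even margins. At least 4 × 5 = 20 must be control cases, which is 20/25 = 80% of all control cancers. At most one type could qualify, and only if it dominated the trial.

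Mean cases per cell, spread evenly:

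- 5 types: 50/(5 × 8) = 1.25 to 75/(5 × 8) = 1.9.
- 10 types: 50/(10 × 8) = 0.6 to 75/(10 × 8) = 0.9.

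If the rates were annual, four years would give 500 × (1 − 0.95⁴) = 93 and 500 × (1 − 0.90⁴) = 172 cases, or about 2-9 per cell in each arm. The Protocol ties the rates to the end of the study, so I do not adopt that reading.

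**Power of the alternative.** If late-stage cancers halve from 12.5 to 6.25 per 500 (2.5% versus 1.25%), Fisher's test per randomised participant has about 24% power.

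**The case against.** Four objections have force.

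- A reader might infer that stage shift is the trial's principal evidence of benefit. The Protocol does not support that. Stage shift is a stated aim and part of the hypothesis, but it is absent from the objectives (section 3.1) and the endpoints (section 4.11), and it is not the powered outcome. This limits the weight of the point.
- A reader might treat the rejection rates as false-positive rates. They are not. In these scenarios the stage mix of detected cancers really does differ, and the test reports that correctly. The per-randomised test answers another question. The error lies in reading the case-only result as late-stage disease averted, and section 8.0 does not attach that reading to the test.
- The larger percentages use the plan's ceiling of 10% and assume that every extra cancer is early and none replaces a late one. At the planned 2-point gain the effect is smaller, and the late-stage share is assumed throughout. Only the range should be quoted.
- It would be too strong to say that the plan ignores randomisation. Section 8.0 compares detection rates between the randomised cohorts, so unequal case totals would be visible.

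On sparsity, the count per cell rests on an assumed number of types and an even spread; a dominant type would have more. The pooled comparison already uses an exact test and is not open to this criticism.

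What remains is that no stage-specific comparison keeps the randomised denominator, and the tests that are fixed cannot separate added early diagnoses from fewer late ones.

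**Conclusion.** The point holds as a weakness in a supporting analysis that should be corrected; it is not a defect of the primary analysis. The case-only tests can turn significant through extra early diagnoses alone, and such a result would not support the clinical-impact aim. Under the stated assumptions (30-60% late in controls, equal late-stage incidence, all extra cancers early) the pooled test favours cfDNA in about 9-21% of trials at 5% versus 7% and 28-66% at 5% versus 10%. A test per randomised participant rejects in about 3-4%. That the tests condition on diagnosis follows from section 8.0 itself; the size of the effect depends on the assumptions.

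The per-type Pearson approximation will fail for most or all cancer types. The requirement of at least 40 cases of one type does not depend on how many types there are; the figure of 0.6-1.9 cases per cell does.

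**What to change.** In section 8.0:

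1. Make the inferential stage analysis the incidence of late-stage cancer per randomised participant, compared by arm and stratified by hereditary cancer syndrome, with early-stage incidence shown beside it.
2. Define early and late stage in advance.
3. Report the stage distribution among diagnosed cancers, overall and by type, as descriptive only. If a per-type p-value is shown, use an exact test instead of Pearson's. Do not offer a case-only ordinal test as evidence of benefit, since it would condition on diagnosis in the same way.
4. State the low power of the per-randomised comparison: about 24% if late-stage cancers are halved from 12.5 to 6.25 per 500.

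The cost is a change of wording. Diagnoses and pathology are already to be collected for all participants in both arms (section 4.8, Collection of Clinical Data). The real price is the low power: a non-significant result must not be read as showing no effect on late-stage disease.
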